23.	Economic Burden to Participants.....	27
24.	Informed Consent	27
25.	Setting.....	28
26.	Resources Available	28
27.	References	28
28.	Protocol Checklist	29

1. Study Summary

Project Title	Dose-Ranging Study of Persons Receiving Doxycycline
Project Design	To determine tissue pharmacology of multiple doses of doxycycline for sexually transmitted infection (STI) post-exposure prophylaxis (PEP), investigators at Emory University will collaborate with the Centers for Disease Control and Prevention (CDC) to conduct a clinical trial of up to 40 people aged 18-59 (at least 12 people assigned male sex at birth (AMAB) and 12 people assigned female sex at birth (AFAB)), with measurement of doxycycline concentrations in the rectum and vagina at study follow-up visits. Enrolled participants will take a total of 5 doses of doxycycline over a 3-week period.
Primary Objective	To determine dose-ranging tissue penetration of doxycycline for STI prevention strategies.
Secondary Objective(s)	N/A
Research Intervention(s)/Interactions	Doxycycline & Biological Specimen Collection
Study Population	Healthy people assigned male or female at birth and are willing to undergo study procedures.
Sample Size	40 participants total 
 • Arm A (100mg Doxycycline): at least 6 AFAB and 6 AMAB with a target sample size of 10 in each group • Arm B (200mg Doxycycline): at least 6 AFAB and 6 AMAB with a target sample size of 10 in each group
Study Duration for individual participants	8 weeks
Study Specific Abbreviations/Definitions	AFAB — Assigned female sex at birth AMAB — Assigned male sex at birth CDC — Centers for Disease Control and Prevention CRAI — Condomless receptive anal intercourse DOX — Doxycycline ED-PrEP — Event-driven pre-exposure prophylaxis HIV — Human Immunodeficiency Virus IDS — Investigational Drug Services MSM — Men who have sex with men PrEP — Pre-exposure prophylaxis PEP — Post-exposure prophylaxis STI — Sexually transmitted infection WHO — World Health Organization
Funding Source (if any)	Centers for Disease Control and Prevention

2. Objectives

The purpose of this study is to collect data regarding the ability of various oral doses of doxycycline to penetrate mucosal tissues in people AMAB and AFAB to inform future studies of combinations of doxycycline to protect against bacterial STIs.

3. Background

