Recent studies have demonstrated the potential utility of single-dose oral doxycycline post-exposure prophylaxis (Doxy-PEP) against bacterial sexually transmitted infections (STIs)^{1,2}. New dosing strategies are being explored that would allow for a single event-driven oral dose of medications that protect from HIV as well as other bacterial STIs. However, the ability of doxycycline to penetrate mucosal tissues and provide protection from STIs remains underexplored. A previous pilot study conducted by the DHP Laboratory Branch at CDC examined the ability of a 200mg oral dose of doxycycline to penetrate the vaginal and rectal mucosa. However, data regarding alternative doxycycline doses and accumulation of doxycycline with multiple doses are lacking^{1,2}.

The purpose of this project is to collect data regarding the ability of various oral doses of doxycycline to penetrate mucosal tissues in people AMAB and AFAB to inform optimization of doxycycline for STI prevention strategies. Results from this study will be compared to results of the previous pilot study conducted by the DHP Laboratory Branch at CDC. The objectives of this project are to conduct a clinical study investigating the pharmacokinetics of two different doses of doxycycline in people AMAB and AFAB where biological specimens are provided to the DHP Laboratory Branch for doxycycline measurement and analysis. Data regarding mucosal drug exposure will help inform development of STI prevention strategies.

Public Health Relevance: Incidence of bacterial STIs are increasing and studies have recently shown that Doxy-PEP can reduce incidence of bacterial STIs among men who have sex with men (MSM) and Doxy-PEP is being explored for STI prevention among women^{3,4}. A better understanding of mucosal drug penetration of doxycycline will inform the design of future studies to prevent STIs in various populations.

4. Study Endpoints

Primary Study Endpoints

1. To compare doxycycline concentrations in rectal tissues collected 24 hours after T¹ dose of 100 mg or 200 mg of doxycycline in AMAB participants.
2. To compare doxycycline concentrations in vaginal tissues collected 24 hours after T¹ dose of 100 mg or 200 mg of doxycycline in AFAB participants.
3. To compare doxycycline concentrations in rectal tissues collected 24 hours after T⁵ dose (visit 8) of 100 mg or 200 mg of doxycycline in AMAB participants.

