4. To compare doxycycline concentrations in vaginal tissues collected 24 hours after T⁵ dose (Visit 8) of 100 mg or 200 mg of doxycycline in AFAB participants.

Exploratory Endpoint

To assess longitudinal doxycycline concentrations in blood, urine, throat, vaginal, penile, and rectal secretions over the 3-week study period in people taking 5 doses of 100mg vs. 200mg of doxycycline.

5. Study Intervention/Investigational Agent

Study Product Description

Doxycycline is used to treat or prevent infections that are strongly suspected to be caused by bacteria; it is an antimicrobial drug indicated for bacterial infections such as sexually transmitted infections.

It will be purchased from the manufacturer and stored at the Emory Investigational Drug Services (IDS).

Dosage, Preparation and Administration of Study Product

[figure not shown]
Doxycycline (DOX) will be given orally at 100 and 200 mg doses. Pharmacy packages will be prepared by an IDS Pharmacist and delivered to the participant by a study team member. Prior to drug dispensing, the clinician will assess participant's medical history, and ensure the participant has no known allergies to the study drug. If a participant reports an allergy and a suitable alternative is not available, then the clinician may opt to not enroll the participant into the study.

Accountability Procedures for the Study Product

The IDS pharmacist will maintain accurate accountability logs at the Hope Clinic.

6. Procedures Involved

Study Schema

Study Visits

All study visits described below apply to both Arms A & B. The only difference between the two will be the dose participants receive (100 mg v. 200 mg). Study participants will be assigned to dosing arms in a sequential manner. Arm A will enroll at least 6 participants AFAB and at least 6 participants AMAB at 100mg prior to proceeding to Arm B. Target enrollment will be n=10 in each group. Arm B will enroll at least 6 participants AFAB and at least 6 participants AMAB at 200mg. Target enrollment will be n=10 in each group.

Recruitment

Potential participants will be identified from one of the recruitment methods (e.g., flyers, social media, advertisements, etc.) mentioned in the recruitment methods section below.

Phone Screening

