Once a potential participant is identified via recruitment methods, study staff may administer a pre-screening questionnaire via phone to assess preliminary eligibility. If the results of the pre-screening questionnaire indicate that the potential participant may be eligible for this study, they will be invited to the clinic to complete the screening visit.

Screening Visit

At this visit, the informed consent will be reviewed, and all questions answered. The participant will sign the consent form prior to completing any study activities. Once the participant signs the informed consent, a study identification number will be assigned. Eligibility will then be determined for each participant based primarily on information gathered during the screening visit. Procedures conducted during the screening visit may include:

- Collection of demographic information
- Collection of medical history
- Collection of current medications
- Physical exam
- Pregnancy test for women of childbearing potential
- Self-collected vaginal and/or rectal swab test for gonorrhea and chlamydia
- Urine specimen to test for gonorrhea and chlamydia
- Blood sample collection - up to 17 mL
 - HIV testing
 - CBC
 - Coagulation Tests
 - Creatinine

Timing of the first doxycycline dose will be denoted at T¹ = 0hr. All subsequent visits should be calculated from this time point. Additional doses will be denoted as T², T³, T⁴ and T⁵.

Visit 1a (Day 0) – Enrollment, Pre-T¹ Dose & T¹ Dosing

This visit should occur ≤ 42 days after the Screening Visit. Participants will count towards the total n of the study upon completion of this visit.

Procedures conducted PRIOR TO DOSING may include:

- Blood Sample Collection – up to 10 mL
- Urine Sample Collection – Urinalysis
- Self-Administered Swab Collection
 - Rectal (x3)
 - Vaginal (x3) – for participants with a vagina only
 - Throat (x2)

Dosing

Doxycycline (Arm A – 100mg; Arm B – 200 mg) will be administered to the participant. This dose should take place while the participant is in the clinic.

Visit 1b (Hour 2-4/Day 0) – Post-T¹ Dose

This visit will take place 2-4 hours after the first dose (T¹ = 0 hr).

Procedures conducted at this visit may include:

- Blood Sample Collection – up to 10 mL
- Self-Administered Swab Collection
 - Rectal (x3)
 - Vaginal (x3) – for participants with a vagina only
 - Throat (x2)

Visit 2 (Hour 24/Day 1) – Biopsy Visit

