This visit will take place 24 hours after the first dose (T¹ = 0 hr). For participants who menstruate, this visit should take place 7-10 days after their last menstrual cycle.

Participants will be asked to abstain from receptive anal and/or vaginal intercourse for 3 days prior to this visit.

Procedures conducted at this visit may include:

- Review of medical history
- Review of current medications
- Symptom-guided physical exam
- Evidence-based HIV/STI risk reduction counseling
- Rapid HIV test (if risk behavior has changed since screening)
- Blood Sample Collection – up to 10 mL
- Urine Sample Collection

Protocol Title: Doxy-PEP

- Urinalysis
- Urine pregnancy test – for women of childbearing potential
- Staff-Assisted Swab Collection
 - Urethral (x1)
 - Glans (x1)
- Self-Administered Swab Collection
 - Rectal (x3)
 - Vaginal (x3) – for participants with a vagina only
 - Throat (x2)
- Rectal Biopsy – *Required for participants who DO NOT have a vagina. This is an optional, additional biopsy for those who do have a vagina.*
 - Rigid sigmoidoscopy
 - Biopsies (2-4 tissue samples)
- Vaginal/Cervical Biopsy – *Required for participants who DO have a vagina.*
 - Speculum insertion
 - Vaginal Biopsies (1-2 tissue samples)
 - Cervical Biopsies (1-2 tissues samples)

All participants will be instructed to place nothing in the rectum and/or vagina and to abstain from intercourse for 7 days after the biopsy procedure to allow the mucosa to heal.

Visit 3 (Hour 48/Day 2)

This visit will take place 48 hours after the first dose ($T^1 = 0$ hr).

Procedures conducted at this visit may include:

- Blood Sample Collection – up to 10 mL
- Urine Sample Collection – Urinalysis
- Self-Administered Swab Collection
 - Rectal (x3)
 - Vaginal (x3) – for participants with a vagina only
 - Throat (x2)

Visit 4 (Hour 72/Day 3) – Pre- T^2 Dose & T^2 Dosing

This visit will take place 72 hours (3 days) after the first dose ($T^1 = 0$ hr).

Procedures conducted PRIOR TO DOSING may include:

- Blood Sample Collection – up to 10 mL
- Urine Sample Collection – Urinalysis
- Staff-Assisted Swab Collection
 - Urethral (x1)
 - Glans (x1)
- Self-Administered Swab Collection

Protocol Title: Doxy-PEP

- Rectal (x3)
- Vaginal (x3) – for participants with a vagina only
- Throat (x2)

Dosing

Doxycycline (Arm A – 100mg; Arm B – 200 mg) will be administered to the participant. This dose should take place while the participant is in the clinic.

Visit 5 (Hour 168/Day 7) – T³ Dosing at Home

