Participant will take dose (Arm A – 100mg; Arm B – 200 mg) at home and provide proof of dosing as described in study-specific procedures.

Visit 6 (Hour 240/Day 10) – T⁴ Dosing at Home

Participant will take dose (Arm A – 100mg; Arm B – 200 mg) at home and provide proof of dosing as described in study-specific procedures.

Study Drug Dispensation Visit (if needed)

If, due to scheduling constraints, menses, holidays, etc., Visit 8 (Biopsy) cannot be completed per protocol, study staff may delay Visits 7a – 12 for up to 4 weeks. In this case, participants would continue to take doxycycline twice a week until the visits could be scheduled. An additional drug dispensation visit may be needed so the participant can pick up study drug.

Visit 7a (Hour 336/Day 14) – Pre-Dose & T⁵ Dosing

This visit will take place 336 hours (14 days) after the first dose (T¹ = 0 hr).

Procedures conducted at this visit may include:

- Blood Sample Collection – up to 10 mL
- Urine Sample Collection – Urinalysis
- Self-Administered Swab Collection
 - Rectal (x3)
 - Vaginal (x3) – for participants with a vagina only
 - Throat (x2)

Dosing

Doxycycline (Arm A – 100mg; Arm B – 200 mg) will be administered to the participant. This dose should take place while the participant is in the clinic.

Visit 7b (Hour 338-340/Day 14) – Post-T⁵ Dose

This visit will take place 2-4 hours after the T⁵ dose and 338-340 hours (14 days) after the first dose (T¹ = 0 hr).

Procedures conducted at this visit may include:

- Blood Sample Collection – up to 10 mL
- Self-Administered Swab Collection
 - Rectal (x3)
 - Vaginal (x3) – for participants with a vagina only
 - Throat (x2)

Visit 8 (Hour 360/Day 15) – Biopsy Visit

This visit will take place 360 hours (15 days) after the first dose ($T^1 = 0$ hr) and 24 hours after T^5 dose.

Participants will be asked to abstain from receptive anal and/or vaginal intercourse for 3 days prior to this visit.

- Review of medical history
- Review of current medications
- Symptom-guided physical exam
- Evidence-based HIV/STI risk reduction counseling
- Rapid HIV test (if risk behavior has changed since screening)
- Blood Sample Collection – up to 10 mL
- Urine Sample Collection
 - Urinalysis
 - Urine pregnancy test – for participants who are able to bear children
- Staff-Assisted Swab Collection
 - Urethral (x1)
 - Glans (x1)
- Self-Administered Swab Collection
 - Rectal (x3)
 - Vaginal (x3) – for participants with a vagina only
 - Throat (x2)

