Vaginal and cervical tissue samples will not be collected in women who are menstruating, pregnant, or have possible cervical or vaginal infection. A pregnancy test will be administered to women of childbearing potential to ensure they are not pregnant. The first vaginal/cervical biopsy will be scheduled 7 to 10 days after their last menstrual cycle.

Twenty-four to forty-eight hours after the procedure, study personnel will call the participants who donated biopsy samples and inquire about symptoms, complications, or adverse events related to study procedures. Participants who report symptoms suggestive of any significant complications will receive advice on seeking care and will be given referrals to appropriate healthcare professionals as needed. This follow-up may be completed over the phone or through electronic communication.

Rectal Mucosal Sampling Procedures

A trained, delegated clinician will be performing all rectal mucosal sampling procedures with the assistance of the study coordinator utilizing a disposable anoscope, rigid sigmoidoscope, light source, and jumbo biopsy forceps.

Then, without the administration of any previous enemas or other preparation, a rigid sigmoidoscope will be inserted and 2-4 (first biopsy) or 8-12 (second biopsy) adequate ~1.0 mm thick biopsy specimens will be taken from normal-appearing rectal mucosa approximately 10 cm above the external anal aperture using flexible sigmoidoscopic forceps mounted on a semi-flexible rod. All biopsy specimens will be coded with a unique numeric identifier such that the laboratories that receive the specimens will be unable to link them back to the study participants. Two to three biopsy specimens will be placed immediately into cryotubes for testing of drug levels at CDC. The remaining biopsy specimens will be placed in media and transported to [name] lab where the specimens will be processed for various laboratory protocols (e.g., bulk and spatial transcriptomics, exogenous hormone treatment for bulk and spatial transcriptomics and explant challenge experiments, or flash-frozen for subsequent quantification of HIV within rectal tissue).

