5. For HIV positive people, on stable antiretroviral therapy with an undetectable viral load and CD4 count > 300ul/ml
6. Willing to use condoms consistently for the duration of the study
7. Able to provide informed consent
8. No plans for relocation in the next 4 months
9. Not pregnant and does not plan on getting pregnant for the duration of the study
10. Willing to undergo peripheral blood, urine, rectal or vaginal secretion collection, and a rectal or vaginal and cervical biopsy procedure
11. Willing to use study products as directed

Exclusion Criteria

1. Current or chronic history of liver disease
2. Continued need for, or use during the 90 days prior to enrollment, of the following medications:
 - a. Systemic immunomodulatory agents
 - b. Supraphysiologic doses of steroids (short course steroids less than 7 days duration, allowable at the discretion of the investigators)
 - c. Chemotherapy or radiation for treatment of malignancy
 - d. Experimental medications, vaccines, or biologicals
3. Intent to use doxycycline or other tetracycline-derived antibiotics during the course of the study, outside of the study procedures
4. Any other clinical condition or prior therapy that, in the opinion of the investigator, would make the patient unsuitable for the study or unable to comply with the study requirements
5. Known allergic reaction to study drugs.
6. Significant laboratory abnormalities at baseline visit for rectal biopsies, including but not limited to:
 - a. Hgb ≤ 10 g/dL
 - b. PTT > 1.5x ULN or INR > 1.5x ULN

- c. Platelet count <100,000

12. Population

This study will not include any of the vulnerable populations listed below.

- Adults unable to consent
- Individuals who are not yet adults (infants, children, teenagers)
- Pregnant women
- Prisoners
- Cognitively impaired or
- Individuals with Impaired Decision-Making Capacity

At the time of enrollment, participants will be asked to complete a demographic form in which they will indicate their sex assigned at birth (male/female), gender identity, ethnicity (Hispanic/Latinx or non-Hispanic/Latinx) and race with which they identify (White, Black/African American, American Indian/Alaska Native, Asian, Native Hawaiian/Other Pacific Islander, and/or Other). Other than sex assigned at birth, this information will be used for descriptive statistics only and not as a variable to explain differences between participants.

13. Vulnerable Populations

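### Does a minimum of 6 per group, counted at first dose, leave the primary tissue comparisons too thin?

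*Combined protocol and SAP*

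**What the plan says.** Section 6 makes Visit 1a (Day 0) the enrolment visit. It ends with the first dose, and the counting rule is "Participants will count towards the total n of the study upon completion of this visit".

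The Study Summary (Section 1) gives each arm "at least 6 AFAB and 6 AMAB with a target sample size of 10 in each group". Section 6, Study Visits, makes the arms sequential: "Arm A will enroll at least 6 participants AFAB and at least 6 participants AMAB at 100mg prior to proceeding to Arm B". Section 14 plans a total of 40, 20 of each sex assigned at birth.

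The four primary endpoints (Section 4) compare the doses within sex assigned at birth. Endpoint 1 concerns concentrations "in rectal tissues collected 24 hours after T¹ dose of 100 mg or 200 mg of doxycycline in AMAB participants". Endpoint 2 is its vaginal counterpart in AFAB participants, and endpoints 3 and 4 repeat the pair 24 hours after the fifth dose (Visit 8). At both biopsy visits, however, anatomy sets the mandatory site. The rectal biopsy is "Required for participants who DO NOT have a vagina" and optional for anyone else.

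Several provisions limit the loss of tissue:
- **Cycle timing:** "The first vaginal/cervical biopsy will be scheduled 7 to 10 days after their last menstrual cycle".
- **Rescheduling:** if Visit 8 cannot go ahead as planned, "study staff may delay Visits 7a – 12 for up to 4 weeks".
- **Eligibility (Section 11):** "No plans for relocation in the next 4 months", no pregnancy or plan for one, and willingness to undergo biopsy (inclusion criterion 10).
- **Screening:** gonorrhea and chlamydia are tested.

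Neither Section 7 (analysis) nor Section 16 (withdrawal) defines an evaluable participant or a replacement rule.

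**The concern.** Every primary endpoint is a tissue concentration, yet a participant fills a place before any tissue has been taken. The protocol itself foresees losses after that point: relocation before biopsy (Section 16), no vaginal or cervical sampling during menses, pregnancy or possible infection (Section 6), and removal for pregnancy (Section 17). A group that closed at 6 would have no reserve, so one missed biopsy would leave 5. An Arm A shortfall at Visit 8 could also come to light after Arm B had opened.

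The anatomy rule adds a second route. An AMAB participant with a vagina, or an AFAB participant without one, could comply fully with the protocol and still not supply the tissue that their group's endpoint uses.

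Precision and power in groups that are already small would be at stake. In the extreme, a comparison could become unable to reach p<0.05 whatever the data.

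**Working it through.** **Stated counts.** Four groups of 6 make 24, which agrees with the minimum of 12 AMAB and 12 AFAB. Four groups of 10 make 40, which agrees with the stated total. There is no power calculation, effect size, variability or dropout rate to reproduce.

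**Assumptions, none from the documents.** A fraction *d* of counted participants lacks the tissue for a given endpoint, independently of one another; *d* is 10% or 20%. Section 7 names neither the non-parametric test nor its sidedness, so I take a two-sided exact rank-sum test.

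**1. Chance of at least 6 tissue results in one group**
- 6 enrolled: (1−*d*)^6. This is 0.9^6 = 53.1% at 10% loss and 0.8^6 = 26.2% at 20%.
- 10 enrolled: P(Binomial(10, 1−*d*) ≥ 6). This is 99.8% at 10% loss and 96.7% at 20%. For all four groups together it is 99.4% and 87.5%.

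So even a group that stops at exactly 6 keeps all 6 results slightly more often than not at 10% loss. The expected numbers are 6 × 0.9 = 5.4 and 6 × 0.8 = 4.8; from 10 they are 9 and 8.

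**2. Can the test still reach p<0.05?** The smallest two-sided exact p-value is 2/C(a+b, a), where a and b are the numbers with tissue in the two arms.

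| Tissue results | Smallest p |
|---|---|
| 6 v 6 | 0.0022 |
| 5 v 5 | 0.0079 |
| 4 v 4 | 0.0286 |
| 3 v 5 | 0.0357 |
| 3 v 4 | 0.0571 |
| 3 v 3 | 0.10 |

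Summing the binomial probabilities of all pairs (a, b) whose smallest p is 0.05 or more gives 0.56% (10% loss) and 8.1% (20% loss) with 6 enrolled per group. With 10 enrolled per group it is below 0.01% at either rate.

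**3. Precision.** The standard error of the between-arm difference relative to 6 v 6 is √[(1/a + 1/b)/(2/6)]. It is 1.095 at 5 v 5 and 1.225 at 4 v 4, so 10% and 22% larger.

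**4. Power.** This is a simulation with lognormal concentrations and a twofold ratio, averaged over the binomial numbers with tissue. The effect and the coefficient of variation (CV) are assumed.

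| Enrolled per group | No loss | 10% loss | 20% loss |
|---|---|---|---|
| 6, CV 50% | 57% | 46% | 38% |
| 6, CV 40% to 80% | 74% to 29% | 63% to 23% | 52% to 19% |
| 10, CV 50% | about 83% | 79% | about 72% |

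At CV 50%, stopping at 6 instead of 10 costs 83 − 57 = 26 points before any tissue is lost. A 10% loss then costs a further 57 − 46 = 11 points. Only those 11 points belong to the counting rule. At the planned 10, the same loss costs about 83 − 79 = 4 points.

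**5. Time cost of counting tissue instead.** If Arm B could open only once Visit 8 tissue was in hand, the earliest date would be Day 15 after the first dose of the last counted participant. With the permitted 4-week delay it would be Day 15 + 28 = Day 43.

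**The case for a change.** The strongest case for a change is that 6 is the only floor the protocol commits to. The Summary says up to 40, and the target of 10 is itself an enrolment figure. None of the safeguards guarantees tissue, and nothing obliges the team to top up Arm A once Arm B is open. A change of wording and a tracking log would cost almost nothing.

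Much of this is true as description. The minimum is an enrolment count, and a group that stops at 6 may have fewer than 6 results. But the floor was never stated as an evaluable number and supports no power or precision claim, so no stated figure is missed. Nothing closes Arm A at 6: further participants can be enrolled up to 10 per group and 40 overall under the present text. A rule that did more would either enrol beyond the plan or hold back Arm B. Holding back Arm B pushes the two doses further apart in calendar time in a study that assigns dose sequentially. That is a debatable exchange for a problem that nearly vanishes at the planned size.

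The difference between anatomy and sex at birth is real, but it exists at any group size and does not depend on when participants are counted. The endpoints already say which tissue from which stratum enters each comparison. A participant who did not give that tissue simply has no value for it, and an AMAB participant with a vagina may still give the optional rectal biopsy. The documents do not say how many such participants to expect.

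**Conclusion.** The observation is correct, but the plan can stand. Counting at first dose does not bias the comparison of doses. It means that a group closed early, at or near 6, may be somewhat less precise than its headline number suggests, chiefly at Visit 8; Visit 2 follows enrolment by a single day, so losses there are probably smaller. With 6 enrolled per group, a Visit 8 comparison would be unable to reach p<0.05 in 0.56% of cases at 10% loss and 8.1% at 20%. With the planned 10, the chance is negligible.

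Analysts will in any case have to report how many tissue results each of the four comparisons uses, and the sponsor can already keep enrolling towards 10 where biopsies are missed. These sizes rest on assumed loss rates, an assumed twofold difference and CV, independent losses and a two-sided exact rank-sum test. Loss well above 20%, or groups deliberately stopped at 6, would make the matter weightier; nothing in the documents indicates either.

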Twenty-four to forty-eight hours after the procedure, study personnel will call the participants who donated rectal biopsy samples and inquire about symptoms, complications, or adverse events related to study procedures. Participants who report symptoms suggestive of any significant complications will receive advice on seeking care and will be given referrals to appropriate healthcare professionals as needed. This follow-up may be completed over the phone or through electronic communication.

Protocol Title: Doxy-PEP

Table 1. Study Schema – Arm A & B

	Screening Visit	Visit 1a	Visit 1b	Visit 2	Visit 3	Visit 4	Visit 5	Visit 6	Visit 7a	Visit 7b	Visit 8	Visit 9	Visit 10	Visit 11	Visit 12
Timepoint (Days)	-42 to 0	0	0	1	2	3	7	10	14	14	15	16	17	18	21
Timepoint (Hours)	-	0	2-4	24	48	72	168	240	336	338-340	360	384	408	432	504
Window	-	-	±2 hr	±2 hr	±2hr	±2 hr	±2hr	±2hr	±2hr	±2hr	±2hr	±2hr	±2hr	±72hr	±72hr
Informed Consent	X														
Physical Exam	X			X ¹							X ¹				
Medical History	X			X ¹							X ¹				
Current Medications	X			X ¹							X ¹				
Screening Labs ²	X														
Pregnancy Test	X			X							X				
Eligibility	X														
Dose Administration		X				X	X ³	X ³	X						
Biopsy				X							X				
Urine Sample	X	X		X	X	X			X		X	X	X	X	X
Rectal & Vaginal ⁴ Swab		X	X	X	X	X			X	X	X	X	X	X	X
Throat Swab		X	X	X	X	X			X	X	X	X	X	X	X
Urethral & Glans Swab				X		X					X		X		
Blood Volume	17 mL	10 mL	10 mL	10 mL	10 mL	10 mL			10 mL	10 mL	10 mL	10 mL	10 mL	10 mL	10 mL

¹Abbreviated/symptom-directed/review during non-screening visits.

²Includes CBC, coagulation, creatinine, HIV testing, urine, and self-collected swab for chlamydia & gonorrhea.

³Dose taken at home.

⁴Vaginal swabs done only on participants with vaginas.

7. Statistical Analysis Plan

Primary Outcomes

Comparisons between time points will be conducted with a non-parametric statistical test of differences in median doxycycline concentrations between the two dosing regimen arms, stratified by sex assigned at birth. P-values less than 0.05 will be considered significant.

Exploratory Outcomes

Exploratory outcomes will be analyzed with various statistical methods to examine changes over time in doxycycline concentrations between the dosing arms, stratified by sex assigned at birth.

8. Data and/or Specimen Banking

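### Section 7 plans only a between-arm test at p<0.05 for the four tissue endpoints; the 200:100 ratio with a 95% interval should be the main result, and the sponsor should confirm what the time-point wording means

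*Combined protocol and SAP*

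**What the plan says.** Section 1 gives a single objective: "To determine dose-ranging tissue penetration of doxycycline for STI prevention strategies". Section 4 turns it into four primary endpoints. The first begins "To compare doxycycline concentrations in rectal tissues collected 24 hours after" the T1 dose and compares the two doses in AMAB participants. The others repeat this for vaginal tissue in AFAB participants and for both tissues 24 hours after the T5 dose (Visit 8).

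Section 7 gives the primary outcomes two sentences. The first says "Comparisons between time points will be conducted with a non-parametric statistical test of differences in median doxycycline concentrations between the two dosing regimen arms". It adds that AMAB and AFAB participants form separate strata. The second says "P-values less than 0.05 will be considered significant". The test is not named, and no effect measure or interval is planned there or elsewhere.

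Three other places bear on the analysis:
- Section 6, Study Visits, sets each sex-by-arm group at a minimum of 6 and a target of 10, and says "Study participants will be assigned to dosing arms in a sequential manner".
- Section 6 fixes the second biopsy visit: "This visit will take place 360 hours (15 days) after the first dose". The drug dispensation paragraph lets Visits 7a to 12 slip by up to 4 weeks and adds "In this case, participants would continue to take doxycycline twice a week until the visits could be scheduled".
- Section 3 says that "data regarding alternative doxycycline doses and accumulation of doxycycline with multiple doses are lacking".

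**The concern.** A dose-ranging objective asks how much more drug reaches the tissue at 200 mg than at 100 mg. The planned output, a p-value against 0.05, does not say. With 6 to 10 per group, p>0.05 can mean that a doubling is ruled out or that the data are too few to tell. These two findings would point later dose work in different directions, and the planned result would report them identically.

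The opening words of the Section 7 sentence add an ambiguity. They announce a comparison of time points, while the rest of the sentence and all four endpoints describe a comparison of arms. Two analysts could run different primary analyses from the same text.

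**Working it through.** **Step 1. Text against endpoints.** Endpoints 1 and 2 are 100 v 200 mg at 24 hours after T1. Endpoints 3 and 4 are 100 v 200 mg at 24 hours after T5. None compares T1 with T5. Reading the phrase as *at each time point* agrees with all four endpoints and with the rest of the sentence.

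**Step 2. Inputs.** From the documents: 6 to 10 per group and a threshold of 0.05 (taken as two-sided). The total reproduces: 2 arms x 2 sexes x 10 = 40, as in Section 14. No effect size, variability, power or precision is stated, so there is no design calculation to reproduce. Assumed: lognormal concentrations with CV 30, 50, 70 or 100%, so that the sd of the logs is sqrt(ln(1+CV²)) = 0.294, 0.472, 0.631 or 0.833.

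**Step 3. Precision and power.** The exact two-sided rank-sum test rejects at U≤23 for 10 v 10 (size 0.043) and at U≤5 for 6 v 6 (size 0.041). Inverting it gives Hodges-Lehmann intervals on log concentration with coverage 95.7% and 95.9%. Simulation (200,000 trials per setting) gives:

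| | CV 30% | CV 50% | CV 70% | CV 100% |
|---|---|---|---|---|
| 95% interval factor, 10 v 10 | 1.33 | 1.59 | 1.85 | 2.26 |
| 95% interval factor, 6 v 6 | 1.48 | 1.88 | 2.33 | 3.06 |
| Power for a true doubling, 10 v 10 | 99.7% | 84% | 59% | 38% |
| Power for a true doubling, 6 v 6 | 93% | 57% | 35% | 22% |

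The factor multiplies and divides the estimate. At CV 50% an estimated ratio of 2.0 would run from 2.0/1.59 = 1.26 to 2.0 x 1.59 = 3.18 at 10 v 10, and from 2.0/1.88 = 1.06 to 2.0 x 1.88 = 3.76 at 6 v 6.

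Check by the t interval on logs, exp(t x sd x sqrt(2/n)), at CV 50%: exp(2.101 x 0.472 x 0.447) = 1.56 for n=10 and exp(2.228 x 0.472 x 0.577) = 1.84 for n=6. Both are slightly narrower than the rank-based factors, as expected.

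**Step 4. Reading a non-significant result.** The table shows the share of non-significant trials whose interval still reaches 2.0.

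| | 10 v 10 | 6 v 6 |
|---|---|---|
| True ratio 1.0, CV 30% | 0.1% | about 6.5% |
| True ratio 1.0, CV 50% | 15% | about 43% |
| True ratio 2.0, CV 50% | 88% | 95% |

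At CV 70 to 100% and 6 v 6, the share with a true ratio of 1.0 is 65 to 79%. There the interval would mainly show that the data are uninformative.

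**Step 5. Reading a significant result.** At CV 50% and 10 v 10, p<0.05 occurs in 40% of trials with a true ratio of 1.5 and in 84% with 2.0. Of the significant trials with a true 2.0, 74% have an interval that includes 1.5. Of those with a true 1.5, about 97% include 2.0.

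**Step 6. Delayed Visit 8.** Doses on days 0, 3, 7, 10 and 14, continued twice weekly to day 42, make 13 doses instead of 5. With first-order decline and an assumed tissue half-life of 1, 3, 7 or 14 days, the 13-dose to 5-dose concentration ratio 24 hours after the last dose is 1.00, 1.02, 1.20 or 1.54.

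**The case against.** **The low-power argument rests on a CV that the documents do not give.** This stands. At CV 30% a doubling is detected with 93% power even at 6 v 6, and a non-significant result nearly does rule it out. A reader might infer that the trial is too small; the documents do not support that, because they state neither the variability nor a target effect. The missing estimate and interval are missing at any CV.

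**The interval will not settle the size of a significant effect.** This stands too. Step 5 shows that it shows the uncertainty but will usually not separate 1.5-fold from 2-fold at these sizes. The main gain is in reading non-significant results.

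**The authors may have wanted a T5 v T1 comparison,** since Section 3 names accumulation as a gap. Possible, so the wording is for the sponsor to confirm. Accumulation in tissue is not an endpoint, and a reader should not infer that Section 7 omits a promised analysis.

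**Medians may be reported anyway, and the estimator is a matter of choice.** A test of differences in medians suggests that medians will appear, but no interval is planned. The Hodges-Lehmann ratio is a typical ratio and equals the ratio of medians only under a pure shift on the log scale.

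**Test and interval can disagree when values fall below the assay limit.** True, because of ties. At 6 v 6, with all six values at 100 mg and one at 200 mg below the limit, the exact p is 0.015 while the lower limit is exactly 1.00.

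**The delayed visits may matter little.** By Step 6 they change Visit 8 levels by 2% or less unless the tissue half-life is about a week or more. A reader might infer that the delay undermines the Visit 8 comparison; the documents give no half-life that would support this.

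**Conclusion.** The point holds as a cheap improvement that should be made before the data are analysed. Section 7 plans a test and no estimate for an objective about amount, and its time-point phrase fits none of the primary endpoints. These two facts come from the text and need no assumption.

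The size of the gain does depend on assumption. Under CVs of 30 to 100%, the interval factor runs from 1.33 to 2.26 at 10 v 10 and from 1.48 to 3.06 at 6 v 6. The gain in reading a non-significant result is small at CV 30% and substantial at CV 50%. Evaluable groups could be smaller than those used here, because participants count at Visit 1a, before either biopsy.

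The interval covers sampling error only. Arms are filled one after the other, so differences in period or in who enrols are not in it.

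**What to change.** Have the sponsor confirm the time-point wording, then replace the first sentence of Section 7 with text to this effect:

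*At Visit 2 and at Visit 8 separately, for rectal tissue in AMAB and vaginal tissue in AFAB participants, the main result is the 200:100 mg concentration ratio with its 95% confidence interval. The exact rank-sum p-value is reported alongside.*

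Add:
- The estimator. Hodges-Lehmann on log concentration is one suitable choice; say that it is a typical ratio, not in general the ratio of medians.
- One value per participant, for example the mean log of replicate biopsies. Section 6 sends two to three rectal specimens for drug levels and takes one or two vaginal biopsies.
- A rule for values below the assay limit (for example tied lowest in the test, half the limit in the ratio, repeated at the limit), with a note that test and interval may then differ slightly.
- A statement that the interval covers sampling error only, because allocation is sequential.

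Optional supportive analyses, as estimates without tests:
- The Visit 8 ratio without participants whose Visit 8 was delayed with extra doses. Groups may become very small.
- The within-participant Visit 8:Visit 2 tissue ratio with 95% interval, by arm and tissue, with the number of missing pairs. At CV 50% and an assumed within-person correlation of 0.5, exp(t x sd x sqrt(2(1-rho)/n)) gives a factor of 1.40 with 10 pairs and 1.64 with 6. In menstruating participants the vaginal ratio also reflects cycle timing: the first biopsy is tied to the cycle, and an undelayed Visit 8 falls 15 - 1 = 14 days later.

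The cost is wording and a little more analysis. No new samples, assays or visits are needed.
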